##### **6.1.6.2 Method and time selection for evaluating, recording and analyzing efficacy parameters**

The subject's Lysholm Knee Score, Tegner Activity Score and VAS will be recorded at preoperative and at postoperative 3 months, 6 months and 12 months, respectively. The soft tissue will get healed around postoperative 6 weeks, and the rehabilitation program allows active exercise after postoperative 1 day. Follow-up visit will be started at postoperative 3 months, and knee function scores were performed at each follow-up point to evaluate the recovery of knee function of the subjects, and MRI will be performed at postoperative 6 and 12 months to evaluate meniscus repair.

## 6.1.7 Safety evaluation approach

### 6.1.7.1 Description of safety parameters

Safety parameters include all adverse events that occur during surgery and follow-up period, surgery-related adverse events, and device-related adverse events (MRI results at postoperative 12 months will be analyzed separately in the form of a list). See the Evaluation and Report of Adverse Events for details.

### 6.1.7.2 Method and time selection for evaluating, recording and analyzing safety parameters

The adverse events that occur during surgery and at postoperative 1 month, 3 months, 6 months and 12 months will be recorded in detail, and evaluated and reported in accordance with the Evaluation and Report Procedure of Adverse Events.

## 6.2 Trial procedure

### 6.2.1 Trial flow chart

For details of the trial procedure, see the following trial procedure and trial flow chart.

### Trial procedure

Assessment	Enrollment and Treatment			Follow Up Visit		
	Baseline	Operation	Post-operation~Discharged	3months	6 months	12 months
Window Period	-14~0d	0d		±15d	±30d	±30 d
Subject Informed Consent	X					
Subject screening registration	X					
Eligibility	X					
Demographics	X					
Physical Examination	X					
Routine Blood	X					
Erythrocyte Sedimentation Rate	X					
Blood Coagulation	X					
Blood/Urine HCG	X					
Electrocardiogram	X					
Lysholm Knee Score	X			X	X	X
Tegner Activity Score	X			X	X	X
VAS	X		X	X	X	X
X-Ray (Knee)	X					

MRI (Knee)	X				X	X
Arthroscopic Exploration		X				
Randomization		X				
Operation		X				
Trial Completion	←		As required (Early Termination)	→		
Adverse Events	←		As required	→		

Notes:

- Examinations on Routine Blood Erythrocyte Sedimentation Rate, Blood Coagulation, Electrocardiogram and X-ray in 14 days prior to the date of surgery (0d) during the screening period are acceptable for baseline assessment.
- Data on Magnetic Resonance Imaging (MRI) in 1 month prior to the date of informed consent is acceptable for baseline assessment.
- During the screening period, the available examination results from standard of care evaluation are acceptable for baseline assessment. After the informed consent form is completed, baseline examination data will be collected for assessing the inclusion and exclusion criteria by investigators.

## 6.2.2 Trial procedure

### 6.2.2.1 Acquisition of the signed informed consent form from subjects

The investigator or his designated personnel will explain to the patient (potential subject) the detailed information related to the investigational medical device and the clinical trial, inform the patient of the possible benefits as well as the known and foreseeable risks, and obtain the signed and dated informed consent form from the patient or his guardian. The investigator must also sign his name and date on the informed consent form.

### 6.2.2.2 Process of Informed Consent

Patients will be subjected to the informed consent process performed by the investigators, and those who agree to participate in this clinical trial will sign an ICF.

### 6.2.2.3 Subject Screening

#### The following data will be collected and assessed during the period of subject screening:

- (1) Collect demographics/history: gender, date of birth, height, weight, history of knee joint related diseases, and injury location;
- (2) Assessment of vital signs: including pulse and blood pressure.
- (3) Specialized Physical Examinations used for the diagnosis of knee meniscus injury, including joint line tenderness, knee motion, and stability assessment including Anterior Drawer Test, Lachamn test, Lever Sign, Bohler Sign;
- (4) Laboratory tests assessment: including blood routine, blood biochemistry (liver function, kidney function, and blood glucose level), blood/urine HCG test.
- (5) X-ray assessment including anteroposterior and lateral views of plain radiographs and full-length weight-bearing radiographs of the lower extremity for using to evaluate fracture, degenerative changes of the knee and episome;

- (6) MRI assessment on the affected knee to determine the type and extent of meniscus injury;
- (7) Record pre-operative Lysholm Knee Score, Tegner Activity Score and VAS of the index knee joint.

#### **8.2.2.4 Arthroscopy Exploration and Surgery**

- (1) Anesthesia and position: After the subject is under epidural, lumbar or general anesthesia, take a supine position according to the investigator's habitual surgical operation procedures, and take on a routine tourniquet to the roof of the index knee joint.
- (2) Surgical incision: Operate according to the standard operating procedure of arthroscopic surgery, and choose the subpatellar and medial lateral approach to the knee joint.
- (3) Exploration: Explore from the suprapatellar bursa, patellofemoral joint, medial compartment, medial malleolus fossa, lateral compartment, posterior medial compartment to posterior lateral compartment, conduct preoperative physical examination and MRI to assess the location of the meniscus tear and determine the repairability of the injury.
- (4) Check inclusion and exclusion criteria, and randomization: Investigator to check if patient is qualified based on arthroscopy exploration result. For the patients who meet all inclusion criteria but none of the exclusion criteria, log in to the central random system to obtain the subject screening code; Patients randomized to the investigational group will be planned to perform surgery using JuggerStitch™, and patients randomized to the control group will be planned to use Fast-Fix 360 (Control Product); Subjects who do not meet the inclusion criteria or meet any of the exclusion criteria will be considered as a screening failure.
- (5) Surgical procedures: during the treatment of meniscus injury, for the combined articular loose body, the loose body should be removed and clean the joint. According to the injury location of meniscus, the probe will be used to determine and select the appropriate meniscal repair system.
- (6) Record the details of medical devices used (model, batch number and quantity, performance evaluation), the treatment of combined injuries;
- (7) Record concomitant medications during the surgery (painkillers and anesthetics by the anesthesiologist excluded));
- (8) Record the device deficiency;
- (9) Monitor and record adverse events during operation and at postoperative.

#### **8.2.2.5 Postoperative rehabilitation and follow-up visits**

- (1) Postoperative treatment: subjects are recommended to use the elastic bandage round limb, appropriate massage to prevent blood clots. After being awake anesthesia, nurse will provide guidance on quadriceps isometric contraction and the straight leg-raising training. See Appendix 9 Postoperative Rehabilitation Guidance.
- (2) Subjects will be followed up in clinical visits at postoperative 3 months, 6 months and 12 months, and Lysholm Knee Score, Tegner Activity Score, and VAS will be obtained at each follow-up visit to assess the recovery of knee joint.
- (3) MRI of the knee joint will be performed at postoperative 6 months and 12 months to evaluate the recovery of meniscus.
- (4) Monitor and record clinical adverse events during each follow-up period for data evaluation and analysis.
- (5) Record the use of analgesic drugs at discharge and during each follow-up period (name of drug, start/discontinuation date, and daily dose).

### **8.2.2.5 Specifications for use of the investigational medical device**

- (1) The correct choice of the type of investigational medical device can minimize the risk of failure of the investigational medical device.
- (2) Meniscal tears not suitable for repair because of the degree of damage (marked irregularity and complex tearing) to the meniscus body including degenerative, radial, horizontal cleavage and flap tears;
- (3) Ensure that the meniscal tissue is properly fixed during surgery. Incorrect fixation of the soft tissue may lead to serious postoperative consequences.
- (4) Proper handling of sutures is very important. Avoid compression or curling injuries caused by the use of surgical instruments such as tweezers or needle holders.
- (5) Excessive force shall be avoided when implanting the investigational medical device to prevent damage to the surrounding tissues or the investigational medical device.
- (6) Properly use the investigational medical device and accessories.
- (7) Use proper fixation devices and follow correct postoperative rehabilitation requirements in the early postoperative period. Incorrect rehabilitation activities in the early postoperative period may lead to failure of the device.

### **8.3 Monitoring plan**

The sponsor shall appoint monitors to regularly monitor the clinical trial institutions participating in this clinical trial to ensure that the clinical trial is carried out in accordance with the trial protocol, the ethics committee's requirements and relevant regulations. The monitor's visit plan is as follows:

- (1) Kick-off meeting of clinical trial institutions: It is carried out after obtaining the approval from the ethics committee and the signing of the clinical trial contract. Its purpose is to ensure that the investigators and their teams receive necessary trainings, fully understand the clinical trial protocol and other project documents, and ensure that all clinical documents and samples are in place prior to the kick-off meeting.
- (2) First subject enrollment visit of clinical trial institutions: The visit is carried out as soon as possible after the first subject of the clinical trial institution is enrolled. Its purpose is to ensure that the enrolled subjects meet the inclusion criteria of the clinical trial and all the required tests are completed, and to confirm that the investigators and their teams fully understand the requirements of the clinical trial, and find and deal with the existing problems in advance.
- (3) Regular monitoring visit of clinical trial institutions: It is carried out after the kick-off meeting and before the end of the clinical trial. The monitoring visit of clinical trial institutions will be carried out every two weeks within the first 2 months of the enrollment period, and once a month thereafter. Its purpose is to ensure that all the enrolled subjects meet the inclusion criteria of the clinical trial, the required tests are completed, and the enrolled subjects are treated smoothly. The data in the case report form and the source data are 100% checked to ensure that thorough settlement of adverse events, and follow-up and treatment of the existing problems. Any changes to the monitoring plan shall be approved by the sponsor in advance.
- (4) Clinical trial close-out visit: It is carried out after all subjects have completed the follow-up, the clinical trial report summary has been formulated and all the existing problems have been properly addressed. Its purpose is to ensure that the investigators and clinical trial institutions fully understand the requirements for clinical trial archiving and the inspections on clinical trials possibly carried out by regulatory authorities.
- (5) The monitor will complete the monitoring visit report after each monitoring visit.

## **7. Statistics Considerations**

## 7.1 Statistical hypothesis testing, statistical method selection and statistical analysis

### 7.1.1 Statistical hypothesis testing

This trial is intended to adopt a prospective, multi-center, randomized controlled design, and its comparison type is a non-inferiority trial. The primary evaluation indicator is set as the difference of Lysholm Knee Score for knee function at 6 months postoperatively.

### 7.1.2 Statistical analysis method

SAS® 9.40 statistical software is used for statistical analysis.

Two-sided tests are used in all statistical tests (unless otherwise specified), and a *P* value of less than 0.05 will be considered as statistically significant.

#### Descriptive analysis:

The count data are described by frequency and percentage; the measurement data are described by mean, standard deviation, median, maximum, minimum, and the 25th and 75th percentiles.

#### Baseline demographic analysis:

Summarize the subject number in each clinical sites, list the loss visit cases. Present the size of different data sets in each group, case distribution in each clinical sites, comparison of total shedding rate and detailed list of incomplete causes. Demographic characteristics (age, gender, etc.), relevant medical history and treatment history of the subjects will be described, and age, gender and other characteristics of the two groups will be compared to measure the comparability of the two groups.

Demographic analysis will be based on full Data Set (FAS)

#### Primary Efficacy analysis:

The efficacy indicators will be analyzed by PPS and FAS.

Statistical analysis of the primary endpoint:

$H_0: \pi_1 - \pi_2 \leq -\Delta$ ;

$H_1: \pi_1 - \pi_2 > -\Delta$

The difference of Lysholm Knee Score at postoperative 6 months from baseline will be compared between the two groups using covariance analysis model, and the modified LS means and 95% confidence interval (CI) of the difference between the two groups at postoperative 6 months from baseline will be estimated. If the lower limit of 95% confidence interval is greater than the non-inferiority margin, the research hypothesis will be established. To investigate the consistency among centers, a covariance analysis model containing interaction terms between centers and groups will be considered on the basis of the above covariance analysis model, and the significance of interaction terms will be judged at the level of 0.10.

#### Secondary Efficacy analysis:

The secondary efficacy indicators will be analyzed by PPS and FAS.

Statistical description and inference of data will select suitable descriptive indicators and hypothesis testing methods according to the characteristics of data.

#### Statistical analysis method for safety:

The incidence of adverse events such as pain, device loosening or detachment, and retear occurring during surgery, as well as immediately, at 3 months, 6 months and 12 months postoperatively will be counted.

The type and frequency of adverse events, and their relationship with the investigational medical device will be described. Cases where the clinical trial is suspended due to adverse events and severe or serious adverse events will be specifically noted.

## 7.2 Calculation of sample size

### 7.2.1 Total sample size

The clinical trial hypothesis is based on several publications [22-26], the difference between Lysholm Knee Score at baseline and postoperative 6 months was 30. It is assumed that the difference between Lysholm Knee Score at baseline and postoperative 6 months after arthroscopic meniscus repair will be 34 for both the experimental group and the control group, the standard deviation is set to 8.00, and the non-inferiority margin is set to 5.1 under 15% of the difference, and the test level  $\alpha$  is set to one-sided 0.025 and  $\beta$  to 0.2. Based on the above assumptions, the sample size of each group is 40. Considering that the clinical dropout rate in the clinical trial process was 15%, it was recommended to include 94 subjects in this trial. The calculation formula and required parameters for sample size are as follows:

$$n_T = n_C = \frac{2(Z_{1-\alpha/2} + Z_{1-\beta})^2 \sigma^2}{(|D| - \Delta)^2}$$

where,  $\alpha$ = Expected standard deviation of control group;  $|D|$ = Pooled variance of the test group and the control group,  $\Delta$ = Non-inferiority test margin.

### 7.2.2 Number of clinical trial cases for each disease and the rationale

Meniscal injury of knee joint will be included in this clinical trial as treatment indications, which is in line with the application scope of the JuggerStitch™, and can evaluate the safety and effectiveness for the repair of meniscal tears. The number of sample size is determined by statistical calculation with reference to the clinical study data of the control device.

### 7.2.3 Minimum and maximum subjects for each clinical trial institution in the multi-center clinical trial and the rationale

This trial will be carried out simultaneously in multiple clinical trial institutions, using a centrally randomized, competitive enrollment design. In principle, the number of cases enrolled in each center will be distributed as evenly as possible to ensure sufficient center representativeness. However, considering the feasibility and the progress of enrollment, the number of cases in each participating institution will be adjusted according to the actual situation to ensure the balance of the size of enrollment of each center as far as possible. For a certain center, the final size of enrollment shall not exceed 50% of the total number of cases.

### 7.3 Level of Significance and Power

The statistical test level  $\alpha$  is set to one-sided 0.025, and the power of test  $1-\beta$  is set to 80%.

### 7.4 Expected dropout rate

The expected dropout rate is not greater than 20%.

### 7.5 Pass/fail Criteria To Be Applied To The Results

The pass or fail of test results is determined from a statistical point of view, which is equivalent to verifying the initial hypothesis testing. For this trial, the primary evaluation indicator is difference of Lysholm Knee Score at baseline and postoperative 6 months, and the test type is a non-inferiority test. If the lower 95% confidence interval of the difference in 6-month Lysholm Knee Score between the baseline and postoperative 6 months in the investigational group and the control group is greater than -8 (the preset non-inferiority margin), it is indicated that the non-inferiority conclusion is valid, and it can be considered that the clinical trial successfully verifies that the JuggerStitch™ can meet the requirements of clinical

application, indicating that the clinical trial results are passed; on the contrary, the non-inferiority conclusion is not valid and the clinical trial results are failed.

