### 12.2 Approval of the clinical trial protocol

This clinical trial must follow the *Good Clinical Practice for Medical Devices*. Before the clinical trial, investigators must submit the clinical trial protocol, ICF and other relevant documents to the medical ethics committee of the hospital where the entity responsible for the clinical trial is located. The clinical trial can only be started after the approval of the ethics committee. Any change to the study protocol can only be implemented after the approval of the ethics committee.

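### Section 7.5 passes the device if the lower 95% limit is above -8, but the trial is sized on a margin of 5.1; a device truly 5.1 points worse would pass about 36% of the time instead of 2.5%

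*Combined protocol and SAP*

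**What the plan says.** The primary endpoint is the change in Lysholm Knee Score from baseline to 6 months, tested for non-inferiority. The margin enters the plan in three places.

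- **Section 7.1.2, Primary Efficacy analysis**, writes the hypotheses with a symbol Δ and gives the rule in words: "If the lower limit of 95% confidence interval is greater than the non-inferiority margin, the research hypothesis will be established". No number is attached.
- **Section 7.2.1, Total sample size**, supplies the number: "the non-inferiority margin is set to 5.1 under 15% of the difference". The assumed gain is 34 points in both arms and the SD is 8.00. It continues: "Based on the above assumptions, the sample size of each group is 40". A 15% dropout allowance brings the total to 94.
- **Section 7.5, Pass/fail Criteria**, says that the device passes if the lower 95% limit of the between-group difference "is greater than -8 (the preset non-inferiority margin"). The same section describes its criterion as one "which is equivalent to verifying the initial hypothesis testing".

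Section 7.3 fixes the operating characteristics: α "is set to one-sided 0.025, and the power of test" is 80%.

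**The concern.** Sections 7.2.1 and 7.5 each call their figure the non-inferiority margin, for the same endpoint, and the figures differ: 5.1 and 8. Section 7.5 presents its rule as the initial hypothesis test. That test is written in terms of Δ, and the only value the document gives for Δ is 5.1.

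The margin is the trial's decision threshold. The section 7.5 value is 57% wider than the planning value (8/5.1 = 1.57). If it is applied, the one-sided 0.025 error rate no longer protects against a 5.1-point loss, and the same result can pass by one section and fail by another. A choice between the two values made after data are available would be open to the charge of picking the margin to suit the result.

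**Working it through.** **Inputs.** From section 7.2.1: SD 8.00, gain of 34 in both arms (true difference 0), margin 5.1 = 0.15 × 34, 40 evaluable per group. From section 7.3: one-sided α 0.025, power 80%. From section 7.5: limit -8. From section 7.4: dropout of up to 20%. The planned analysis is a covariance model, but its residual SD is not given, so the main figures use an unadjusted two-sample comparison at SD 8.

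**1. Which margin does the sample size support?** The section 7.2.1 formula with D = 0 is n = 2(z₀.₉₇₅ + z₀.₈₀)²σ²/Δ².

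- Δ = 5.1: 2 × (1.96 + 0.8416)² × 64/26.01 = 38.6, so 39. The t-based calculation gives 40, the plan's figure.
- Δ = 8: 2 × (1.96 + 0.8416)² × 64/64 = 15.7, so 16. The t-based calculation gives 17.

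At 40 per arm and no true difference, power by the noncentral t distribution is 80.4% against 5.1, which matches section 7.3, and 99.3% against 8. The sample size and power statements therefore fit 5.1 and do not fit 8.

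**2. Where do the two rules disagree?**

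- Standard error = 8 × √(2/40) = 1.789.
- Half-width of the 95% interval = t₀.₉₇₅,₇₈ × 1.789 = 1.991 × 1.789 = 3.56.
- Smallest passing difference under -5.1: -5.1 + 3.56 = -1.54.
- Smallest passing difference under -8: -8 + 3.56 = -4.44.

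An observed difference between about -4.4 and -1.5 passes section 7.5 and fails against 5.1.

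**3. Probability of passing** (SD 8, 40 per arm, noncentral t):

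| True difference | Limit -5.1 | Limit -8 |
|---|---|---|
| 0 | 80.4% | 99.3% |
| -3 | 21.2% | 78.8% |
| -5.1 | 2.5% | 36.0% |

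A simulation of 200,000 trials at a true difference of -5.1 gave 36.0% and 2.5%. With identical devices, 99.3% - 80.4% = 18.9% of trials would get opposite verdicts from the two rules.

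**4. Sensitivity of the 36%** (true difference -5.1, limit -8):

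| Evaluable per arm | SD | P(pass) |
|---|---|---|
| 38 (20% dropout: 94 × 0.80 = 75.2) | 8 | 34.4% |
| 47 (no dropout) | 8 | 41.3% |
| 40 | 6 (assumed) | 56.9% |
| 40 | 10 (assumed) | 24.9% |
| 40 | 15 (assumed) | 13.4% |

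If baseline adjustment lowers the residual SD, the figure rises: an assumed baseline–outcome correlation of 0.3 gives 38.9%, and 0.5 gives 45.6%. It stays well above 2.5% in every case examined.

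**The case against.** The strongest reply is that -8 may be the intended margin. Section 7.5 exists to define success and calls -8 preset. A rule set at -8 holds one-sided 0.025 at a true deficit of 8, so on that reading the fault is a mis-sized trial and not an inflated error rate. It is correct that the contrast of 36% with 2.5% depends on 5.1 being the margin. But the alternative would make the stated margin, the 15% rule, the 40 per group and the 80% power all wrong, and it would leave 8, about 24% of 34, with no derivation. The value 5.1 needs only one correction. Under either reading the plan has to be amended.

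Three smaller points stand without changing the conclusion.

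- The basis for 5.1 is itself thin. Section 7.2.1 also cites a published gain of 30, and 15% of that is 4.5. This does not support 8.
- The 80% power against 5.1 holds at 40 evaluable per arm and SD 8. It is 78.3% at 38 per arm, 61.5% at SD 10 and 32.3% at SD 15.
- The planned covariance analysis makes the unadjusted figures illustrative.

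A separate statistical analysis plan, to which sections 7.7 and 7.8 refer, might state one margin. It would still leave sections 7.2.1 and 7.5 in conflict, and section 7.8 says that in principle the main analysis principles and methods will not change.

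**Conclusion.** The pass/fail limit in section 7.5 is wrong as written and must be corrected before the primary analysis. The planning margin is 5.1: it is the only value with a derivation and the only one consistent with the sample size, the power statement and the hypotheses to which section 7.5 refers back. Against that margin, the -8 rule raises the chance of passing a device truly 5.1 points worse from 2.5% to 36.0%. This assumes SD 8, 40 evaluable per arm and no covariate adjustment. Over the dropout and SD values examined, the figure ranges from about 13% to 57%.

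**What to change.** In section 7.5, replace -8 with -5.1. In section 7.1.2, state Δ = 5.1 and say that success requires the lower limit of the two-sided 95% interval (investigational minus control) to be above -5.1. The hypotheses, sample size, power statement and decision rule then share one margin. If the sponsor did intend 8, it would have to justify that value clinically and redo section 7.2.1.

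The cost is a protocol amendment to the primary success criterion. Section 12.2 requires: "Any change to the study protocol can only be implemented after the approval of the ethics committee". Section 14.2 adds submission to regulators where required. The criterion becomes stricter. No extra patients are needed, because the 80% power was already calculated against 5.1. That power still depends on 40 evaluable per arm and SD 8; section 7.4 allows for more dropout than the sizing did ("The expected dropout rate is not greater than 20"% against 15%), and at 38 per arm power is 78.3%.

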## Protocol Synopsis

Clinical Trial Title	A Prospective Multi-Center, Randomized Controlled Pre-Market Clinical Trial to Evaluate the Safety and Efficacy of JuggerStitch™ Meniscal Repair Device on Arthroscopic Meniscal Repair
Protocol Number	CEA2020-26SM
Investigational Device	JuggerStitch™ Meniscal Repair Device (Herein after referred to as JuggerStitch™)
Phase of Clinical Trial	Pre-market
Clinical Trial Design	Prospective, multi-Center, randomized controlled pre-market clinical trial
Control Device	Fast-Fix 360 Meniscal Repair System (Herein after referred to as Fast-Fix 360)
Number of Clinical Trial Institutions	5 clinical sites
Sample Size	94 subjects, 47 cases in investigational group and 47 cases in control group
Indications	Repair of Meniscal Tears
Primary Objective of the Clinical Trial	To evaluate the clinical safety and efficacy of the JuggerStitch™ Meniscal Repair Device on arthroscopic meniscal repair by comparing with Fast-Fix 360 Meniscal Repair System.
Primary Endpoint	Lysholm Knee Score at postoperative 6 months
Secondary Endpoints	(1) Immediate device success rate postoperatively; (2) Lysholm Knee Score at postoperative 3 months and 12 months; (3) Tegner Activity Score at postoperative 3 months, 6 months and 12 months; (4) Visual analogue scale (VAS) score for pain at postoperative 3 months, 6 months and 12 months; (5) Meniscus healing evaluated by Magnetic Resonance Imaging (MRI) scans at postoperative 6 months and 12 months; (6) Device-related adverse event rate.
Inclusion Criteria	(1) 18~60 years old (18 and 60 inclusive); (2) Patient who are scheduled for meniscal repair with a vertical longitudinal full-thickness tears (e.g. bucket-handle) in the red-red and red-white zones; (3) Patients who can understand all risks and benefits described in the informed consent form (ICF), and are willing to comply with the guidance for rehabilitation, and the follow-up visits specified in the clinical trial protocol, and voluntarily participate in the trial and sign the ICF;

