## 5. Objective and Content of Clinical Trial

### 5.1 Objective

The clinical safety and efficacy of the JuggerStitch™ in repair of meniscal tears are assessed by comparing the clinical data of the Fast-Fix 360.

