#### 5.2.1 Primary Endpoints

Lysholm Knee Score at postoperative 6 months.

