#### 5.2.1 Secondary Endpoints

- (1) Immediate device success rate postoperatively;
- (2) Lysholm Knee Score at postoperative 3 months and 12 months;
- (3) Tegner Activity Score at postoperative 3 months, 6 months and 12 months;
- (4) Visual analogue scale (VAS) score for pain at postoperative 3 months, 6 months and 12 months;
- (5) Meniscus healing evaluated by Magnetic Resonance Imaging (MRI) scans at postoperative 6 months and 12 months;
- (6) Device-related adverse event rate.

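### The pass rule declares the device fit for clinical application on the Lysholm result alone, while the safety half of the comparative objective gets no between-arm estimate or interval

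*Combined protocol and SAP*

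**What the plan says.** The synopsis gives the primary objective as "To evaluate the clinical safety and efficacy of the JuggerStitch™ Meniscal Repair Device on arthroscopic meniscal repair by comparing with Fast-Fix 360". Section 5.1 repeats that safety and efficacy "are assessed by comparing the clinical data of the Fast-Fix 360". The objective is therefore comparative for both.

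The only primary endpoint is "Lysholm Knee Score at postoperative 6 months" (section 5.2.1). Safety enters the endpoint list as the last secondary item, "Device-related adverse event rate".

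Under the safety heading of section 7.1.2, adverse events such as pain, loosening or detachment, and retear occurring during surgery, "as well as immediately, at 3 months, 6 months and 12 months postoperatively will be counted". The paragraph continues: "The type and frequency of adverse events, and their relationship with the investigational medical device will be described". It adds that serious events, and cases stopped because of events, will be noted. It names no difference between arms, no confidence interval and no test.

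Section 7.5 takes one input, the lower 95% confidence limit for the difference in Lysholm change. If that limit clears the margin, "it can be considered that the clinical trial successfully verifies that the JuggerStitch™ can meet the requirements of clinical" application, and the trial is passed.

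Section 7.9 assigns safety to the Safety Set, which it words as subjects who used the investigational device and have at least one safety result.

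**The concern.** A non-inferiority result on a mean knee score supports a statement about that score. Section 7.5 draws a broader one, on fitness for clinical use, in a trial meant to support registration in China (section 4.2). The safety half of the objective feeds neither a comparative estimate nor that conclusion.

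The gap matters because device failures occur in a minority of knees. If a fraction more knees fail in one arm, the mean score falls by that fraction times the loss in a failed knee. This can be well inside the margin even when the excess in failures would concern a surgeon. A reader given a pass and a table of counts cannot see what difference in device events the trial leaves open.

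**Working it through.** **The plan's own figure.** Inputs from section 7.2.1: margin 5.1, SD 8, true difference 0, one-sided alpha 0.025, power 80%.

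- n per arm = 2 × (1.960 + 0.842)² × 8² / 5.1² = 38.6, so 39 by the normal formula. With the t distribution, power is 79.4% at 39 and 80.4% at 40, which matches the stated 40.
- Dropout: 40 / 0.85 = 47.06, taken as 47 per arm and 94 in total.

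The sample size thus rests on Lysholm alone. The plan states no safety precision or power, so there is none to reproduce.

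**Does a Lysholm pass exclude a higher event rate?** Assumed, because the documents give no such values: retear 20% with JuggerStitch and 10% with Fast-Fix 360, and a gain smaller by d = 10 or 15 points in a retorn knee. The only failure rate the documents give for the control family is 22.4%, from a systematic review that defined failure as reoperation (section 4.2).

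- Mean deficit = (0.20 − 0.10) × d = 1.0 or 1.5 points.
- SD: either 8, or widened by the failures to √(64 + ½ × (0.10 × 0.90 + 0.20 × 0.80) × d²), which is 8.75 for d = 10 and 9.60 for d = 15.
- Standard error = SD × √(2/40); pass probability from the noncentral t with 78 degrees of freedom and noncentrality (margin − deficit) / standard error. Example: d = 15, SD 8, margin 5.1 gives (5.1 − 1.5) / 1.789 = 2.01.

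| Scenario (40 evaluable per arm) | Pass at margin 5.1 (section 7.2.1) | Pass at margin -8 (section 7.5) |
|---|---|---|
| No excess retear, SD 8 | 80% | 99% |
| 20% v 10%, d = 10, SD 8 / widened | 62% / 54% | 97% / 94% |
| 20% v 10%, d = 15, SD 8 / widened | 51% / 38% | 95% / 85% |

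Both margins are shown because sections 7.2.1 and 7.5 disagree. That conflict is a separate matter, and the point here holds under either value.

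**What would a between-arm estimate show?** At 47 per arm:

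- 20% v 10%: half-width = 1.96 × √(0.10 × 0.90/47 + 0.20 × 0.80/47) = 0.143, so roughly −4 to +24 percentage points around an observed 10.
- Summing over the binomial outcomes of both arms, a Newcombe 95% interval excludes zero on the adverse side in about 25% of such trials.
- Equal rates in both arms: half-width about ±9 points at an assumed 5% and ±17 points at 22.4%.

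**The case against.** Several objections have weight.

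- **Descriptive safety is normal at this size.** This stands. Power to detect a doubling from 10% is only 27% at 47 per arm. But a risk difference with an interval is itself descriptive. The difficulty is descriptive safety combined with a conclusion on clinical application that does not refer to it.
- **Inference is promised elsewhere.** Section 7.1.2 says "Statistical description and inference of data will select suitable descriptive indicators and hypothesis testing methods according to the characteristics of data". That sentence sits under secondary efficacy, on the PPS and FAS, whereas safety is assigned to the Safety Set. Even if stretched to the device-related event rate, it names no estimate or interval.
- **Safety is not absent from the trial.** This also stands. Section 7.5 opens by calling pass or fail a statistical determination, section 17 requires the report to cover adverse events and a conclusion, and section 6.1.5.3 makes serious safety problems a ground for stopping. None of these changes the conclusion that section 7.5 draws once the Lysholm limit is met.
- **The Lysholm test does react to failures.** At margin 5.1 the pass probability falls from 80% to 38–62% in the illustration. That is some protection, but far from exclusion, and at -8 little of it remains.

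A reader might also infer that events will be counted repeatedly across visits. The documents do not say so: section 7.1.2 refers to events occurring at five time points, and section 13.1.4 records each event with its dates. The plan simply does not state that each subject is counted once.

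**Conclusion.** The point holds as a mismatch between what is tested and what is concluded. The comparative safety objective has no comparative estimate, and section 7.5 concludes on clinical application from Lysholm alone. The primary test itself is unaffected. In the illustration a doubled retear rate still passes in about 38–62% of trials at margin 5.1 and 85–97% at margin -8. These figures depend on the assumed retear rates and score loss, on 40 evaluable subjects per arm, and on the planned SD of 8 with or without widening.

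A stronger reading is tempting: that a device with clearly more retears would be passed against the trial's own safety data. That is not supported. At 20% against 10% the interval would include zero in about three trials of four, so it would seldom contradict the pass. What it would show is how large a difference the trial cannot rule out. Nor does the point require safety to become a pass criterion.

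**What to change.** 1. In the safety part of section 7.1.2, report by arm the number and percentage of subjects with at least one event from surgery to 12 months, each subject counted once. Give the risk difference (JuggerStitch minus Fast-Fix 360) with a 95% Newcombe interval for device-related adverse events, the listed secondary endpoint. Do the same for retear and for device loosening or detachment, as recorded adverse events.
2. Word the Safety Set in section 7.9, and device-relatedness in section 13.1.1, so that they cover subjects treated with either study device. Read literally, the Safety Set is limited to users of the investigational device and an adverse device effect is tied to an investigational device, which leaves no control denominator.
3. In section 7.5, limit the pass statement to non-inferiority in change of Lysholm score from baseline to 6 months. State that any conclusion on clinical application is drawn together with the safety differences.

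No safety threshold, safety test, extra visit or larger sample is proposed. The cost is some table rows, two definitions and a rewritten conclusion. The headline claim becomes narrower and the safety intervals will be wide. The retear and loosening rows also depend on consistent recording: section 13.1.4 asks for all adverse events, while section 13.4 says that those judged unrelated will not be reported or followed, and the two must be reconciled.
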